## 6.7 Pathology

All subjects will be scheduled to undergo a breast biopsy (core / excisional / lumpectomy) of the mass or region of abnormality or mastectomy within 30 days after the US study procedure. The date of the biopsy and the pathology results will be recorded. An experienced pathologist will complete a worksheet for each biopsy specimen. If the patient undergoes a surgical biopsy at TJU, the surgeon will mark the transaxial plane of the lesion by sutures upon excision of the breast mass. At UCSD surgical biopsy specimens will be treated according to clinical standard i.e., the imaging plane and the pathology sections will not be matched. Careful attention will be paid to the labeling of each section to ensure the correct orientation. Whole mount paraffin blocks will be prepared from which central 5 mm sections will be cut and mounted on 2 x 3 inch glass slides and stained with hematoxylin and eosin (H&E) according to standard methods and examined microscopically by the pathologist as part of the patient's clinical care. Apart from diagnosis, the pathologist will provide the following variables: estrogen progesterone and HER2 receptor presence or absences; presence or absence of hemorrhagic, necrotic, or other component of the lesion (and their location if present); histological margins; lesion size; TNM staging; histological lesion type; presence or absence of vascular invasion; histological and cytological grade; presence or absence of metastases; node staging; and percentage of the lesion that was invasive or *in situ*. If the

patient undergoes a core biopsy, it will not be possible to assess lesion size. All other histopathological parameters will be the same as for the excisional biopsy described above and the specimens will be treated identically.

In a subset of cases at TJU (approximately 85) staining will also be performed for an immunohistochemical predictor of tumor angiogenesis, specifically a monoclonal antibody against the PECAM endothelial cell marker (anti-CD31; Dako Corporation, Carpinteria, CA) in addition to the standard H&E staining described above. The PI, as part of previously NIH and DOD funded projects, has developed the necessary software for quantitative analysis of contrast enhanced US images and specimens stained with CD31 using a histomorphometry system based on an SMZ-10A microscope (magnification 100x; Nikon, Melville, NY) and ImagePro Plus software [Chaudhari et al. 2000; Forsberg et al. 2008]. Vessels will be identified in the digitized image by the presence of CD31 staining. ROIs around visible vessels will be defined for the ImagePro software. This labor-intensive task will be performed by a graduate student under the direct supervision of the PI. A pathologist will be available for consultation ([name]).

## 6.8 Safety Assessments

Adverse events will be monitored during the entire procedure. Specifically, the patient will be monitored with non-leading questions to monitor the patient for the transient side effects that are described below.

### 6.8.1 Risks/Benefits Assessment.

Serious cardiopulmonary and allergic reactions including fatalities have occurred during or following administration of Definity, causing the FDA to place a black box warning on the agent. However these occurrences have been rare (less than 1 in 5,000 patients). As a result, patients with cardiac shunts or unstable cardiopulmonary conditions will be excluded. Patients will also be monitored for 30 minutes after contrast administration for any adverse reactions. The majority of adverse events from Definity were mild to moderate in severity. Transient side effects that have been described as possibly related to Definity administration include headache (2.3%), back and renal pain (2.1%), flushing (1.1%) and nausea (1.0%). Hypersensitivity reactions to perflutren may occur, although rare.

The use of an intravenous needle and the fluids given through the needle may cause minor discomfort, bleeding under the skin (bruise), and possible infection at the site of needle insertion.

Clinically significant adverse effects from the administration of Definity are unlikely. The use of contrast with the new US imaging techniques is expected to provide significantly more information than from conventional US techniques. This may lead to additional information about the characteristics of breast tumors which may be clinically relevant.

To minimize and/or eliminate risks a nurse will be present during the entire procedure. Adverse events will be monitored during the entire procedure.

The risk benefit ratio is low. Based on the available non-clinical and clinical safety data and the anticipated dose levels of Definity that will be used in this study, safety concerns are minimal. The potential side effects related to Definity administration are described above. In a relatively healthy outpatient population referred for surgical breast biopsy we do not expect any severe reactions. However, in order to ensure that the 20  $\mu$ l/kg dose used for SHI is not altering the risk benefit ratio, data from the first ten (10) patients and then the next ten patients (i.e., the first 20 subjects) will be scrutinized by the TJU DSMB immediately upon completion. If AEs are encountered to a higher degree than what is expected given the Definity label, the dosing will be adjusted downward.

#### 6.8.2 Adverse Events

An AE includes any condition that was not present prior to trial treatment, but appeared following initiation of trial medication; any condition that was present prior to trial treatment, but worsened during trial medication; or any condition, of which the subject has a history, that was not present prior to trial medication initiation but reappeared following administration of Definity. This would include conditions that are likely to be associated with an underlying or intermittent disease (e.g., angina, flu, etc.).

The subjects will be monitored for AEs during the entire procedure. All AEs, including both observed or volunteered problems, complaints, signs or symptoms, and diagnoses, occurring from the initiation of Definity dosing until the completion of the Definity administration will be recorded on a serious or non-serious AE data form, whether or not associated with the use of the trial medication. All adverse events are reported to the Clinical Research Management Office (CRMO) via the password protected Kimmel Cancer Center Adverse Event Reporting System. In addition all unexpected and serious adverse events (SAEs) are reported to the TJU IRB and to the Food and Drug Administration (FDA) if applicable. The investigator is required to submit all unexpected and serious adverse events to the TJU IRB and the DSMB within 48 hours. Fatal adverse events related to treatment which are unexpected must be reported

within 24 hours to the TJU IRB and the DSMB through CRMO. Fatalities not related to the study drug/device must be reported within 5 days.

The AE forms will include: subject identification number and initials; subject's date of birth, gender, and ethnicity; date of Definity administration; signs/symptoms and severity; date of onset; date of resolution or death; relationship to the study drug; action taken; concomitant medication(s) including dose, and route and duration of treatment.

Whenever possible, the AE will be evaluated and reported as a diagnosis rather than individual signs and symptoms. If a definitive diagnosis is not possible, the individual signs and symptoms will be recorded. The investigator will evaluate and note the duration, intensity, and relationship to (association with) the Definity administration, the action taken, and the determination of seriousness for each AE.

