#### 6.3 Ultrasound Imaging

The US examinations will be performed by a qualified sonographer. Procedures and equipment for this trial will be used in accordance with typical clinical procedures. In particular, the mechanical index will be set to less than 0.8 on the US scanner. All trial procedures will be conducted in accordance with Good

Clinical Practice. For the ultrasound examination, the patient will be asked to lie in the supine position and a catheter will be placed in a superficial vein (preferably an antecubital vein). Acoustic coupling gel will be applied to the breast area of interest. A baseline US grayscale scan will be used to identify the mass or abnormal area seen by mammography (or another concomitant imaging mode such as US or MRI). Standard PDI of the lesion or target area will also be performed.

Following baseline imaging, patients will receive a bolus, IV injection of 0.25 ml of Definity and the mass or area of abnormality will be imaged with the broad bandwidth linear array (selected in the development phase described above) and a 30 to 40 second digital clip of the 3D pulse inversion HI volume data, covering baseline to beyond peak enhancement, will be acquired. The point of maximum enhancement in the pulse inversion harmonic images will be assessed visually (by the on-site investigators in consensus) and at least 10 seconds of data will be acquired past this time point. Subsequently more sweeps of the abnormality will be stored on the scanner hard drive every 1 to 2 minutes through the period of enhancement (up to 5 minutes).

After a 30 minutes waiting period patients will receive a second bolus, IV injection of up to 20  $\mu$ l/kg of Definity, sweeps of the mass or abnormal area will be made to acquire 3D SHI grayscale volume data through the period of enhancement (up to 2 minutes in our pilot study). It should be noted, that all subjects will be closely monitored by a physician during and following the study (for 30 minutes as recommended by the FDA) [FDA Alert 2007/2008]. Additionally, resuscitation equipment and trained personnel will be in immediate proximity to the patient during the study.

All images (baseline and contrast-enhanced) will be obtained using a broad bandwidth, 3D, linear array, and will include images of the entire area of interest. The entire examination will be recorded as digital loops, as well as on VHS videotape.

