#### 6.4 Safety Monitoring

Patients will be monitored for AEs during and 30 mins after contrast administration. All other procedures will be performed according to TJU/UCSD standard of care.

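### Section 6.8.2 stops adverse-event form recording when Definity administration ends, so none of the required 30-minute observation after the SHI bolus falls inside the recording window

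*Combined protocol and SAP*

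**What the plan says.** **Recording.** Section 6.8.2 puts on the serious or non-serious AE form those events "occurring from the initiation of Definity dosing until the completion of the Definity administration will be recorded".

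**Observation.** Section 6.4 states: "Patients will be monitored for AEs during and 30 mins after contrast administration". Section 6.8.1 repeats it: "Patients will also be monitored for 30 minutes after contrast administration for any adverse reactions". Section 6.3 adds that "all subjects will be closely monitored by a physician during and following the study (for 30 minutes as recommended by the FDA").

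**Order of dosing.** The 0.25 ml HI bolus comes first. Section 6.3 then says: "After a 30 minutes waiting period patients will receive a second bolus". This second bolus is the SHI dose of up to 20 µl/kg. Section 5.1 caps the total at 1.5 ml per patient.

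**Other wording on AEs.** The definition in 6.8.2 covers a new condition that "appeared following initiation of trial medication" and sets no end point. The sentence after the recording rule reads: "All adverse events are reported to the Clinical Research Management Office (CRMO"). It also has no time limit. The serious adverse events part of 6.8.2 requires a written report of any serious event during the study. Appendix A asks for all AEs in the final report to the IRB.

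**Use of the counts.** To check the SHI dose, section 6.8.1 has the DSMB examine "data from the first ten (10) patients and then the next ten patients (i.e., the first 20 subjects"). The dose goes down if AEs are more frequent than the label would lead one to expect. Section 7.2 describes no AE analysis.

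**The concern.** The plan has staff watch patients for 30 minutes after the last injection, but its form rule closes at the start of that period. The gap falls on the dose that the DSMB is asked to judge. If the DSMB's figures, or the final AE rates, come from forms kept strictly to the 6.8.2 window, non-serious events after the SHI bolus are under-counted. A rule that lowers the dose when AEs are too frequent would then lean towards leaving it unchanged.

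The form is also where onset, severity and relationship to Definity are recorded. An event kept off it may lack the attribution that a dose check needs. Section 1.1 says that the non-serious effects usually last only a few minutes, so they are hard to reconstruct later.

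**Working it through.** The plan gives no figure to reproduce. The check compares the recording and observation windows, then illustrates the possible size.

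**1. The windows, using the order of dosing in 6.3**

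| Period | Observed (6.3, 6.4, 6.8.1) | Inside the 6.8.2 form window |
|---|---|---|
| HI bolus, 0.25 ml | yes | yes |
| 30-minute wait | yes | yes |
| SHI bolus | yes | yes |
| 30 minutes after the SHI bolus | yes | no: 0 of 30 minutes |

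The 10 ml saline flush in 5.1 does not change this. Whether or not it counts as administration, the form window closes where the 30 minutes begin. Section 6.4 names administration and the 30 minutes after it as separate periods, so reading administration as the whole visit is not natural.

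**2. How much of the dose is affected**

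At full dose, SHI bolus = min(20 µl/kg × weight, 1.5 − 0.25 ml).

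- 50 kg: 1.0 ml. This is 1.0/0.25 = 4 times the first bolus and 1.0/1.25 = 80% of the total.
- 60 kg: 1.2 ml. This is 4.8 times, and 1.2/1.45 = 83%.
- 62.5 kg and above: 1.25 ml. This is 5 times, and 1.25/1.5 = 83%.
- Below 50 kg the multiple is smaller: at 45 kg, 0.9 ml and 3.6 times.

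These are volumes. They show which dose is exposed to the gap, not how many events are lost.

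**3. Illustration of the possible loss**

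The documents give no AE rate for the 30 minutes after the last bolus, so a rate r is assumed from Table 1 in section 1.1:

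- Low: headache alone, 40/1716 = 2.3%.
- High: headache, back/renal pain, flushing and nausea, (40 + 20 + 19 + 17)/1716 = 96/1716 = 5.6%. A patient with two reactions counts twice.

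Let u be the share of these events that no route captures. The expected number of patients with an unrecorded event is n × r × u. The chance of missing at least one among the first 20 patients is 1 − (1 − r × u)^20.

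| u | Of 20 patients | Of 450 patients | At least one missed in 20 |
|---|---|---|---|
| 1 (no other capture) | 0.5 to 1.1 | 10 to 25 | 38% to 68% |
| 0.5 | 0.2 to 0.6 | 5 to 13 | 21% to 43% |
| 0 (all captured elsewhere) | 0 | 0 | 0% |

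With the low rate rounded to 2.3%, the 38% becomes 37%.

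**4. Other routes for the same events**

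- Serious events: covered throughout the study.
- Non-serious events to the research office: all are to be reported, but no collection period is stated.
- Non-serious events to the DSMB: 6.8.2 sends it unexpected and serious events within 48 hours. For expected, non-serious events the only stated route is the review of the first 20 patients, whose data source is not defined.

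**The case against.** The best defence is that the sentence is loose drafting and that nobody would follow it literally. The forms carry an onset date separate from the date of dosing, which is of little use if every recorded event starts before the last injection ends. Relationship is to be recorded on a data form with no time limit. Few site staff would stop recording just as their mandatory 30-minute watch begins. This is a fair guess about practice. It does not override the one sentence that states a window, and no other text extends that window.

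A second defence is that the dose rule is not tied to the forms. It speaks of AEs encountered, and events seen during observation are encountered. This stands in part: the lean in the dose rule arises only if the DSMB sees form data cut at that window, and the plan does not say so. The plan does not rule it out either.

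A third defence concerns the size. The top row of the illustration requires staff to observe an event, leave it off the form and also break the instruction to report all AEs to the research office. The middle row has no basis in the documents. The assumed rates are for any timing, and none of the events is allotted to the first bolus. Table 1 gives back/renal pain as 1.2%, whereas the text of 1.1 and 6.8.1 gives 2.1%. All of this is correct. The figures show a range under stated assumptions and are not an estimate. The inconsistency and its remedy do not depend on them.

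**Conclusion.** The concern holds and should be fixed. Section 6.8.2 conflicts with the 30-minute observation in 6.3, 6.4 and 6.8.1, and with its own unlimited reporting sentence. A non-serious event in the half hour after the SHI bolus is off the form under one sentence and reportable under the next. That the form window covers none of those 30 minutes follows from the text with high confidence.

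An actual under-count is possible but not certain. It depends on how sites read 6.8.2 and on which record feeds the DSMB review and the final AE rates. Under the assumed rates, the expected loss in the first 20 patients runs from zero, if the research office captures everything and its reports are used, to about one patient, if nothing else captures these events. Serious AEs are covered and the diagnostic comparisons are not affected.

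**What to change.** Amend the recording sentence in 6.8.2 so that all AEs go on the AE forms from the first injection through at least 30 minutes after the last one. This matches 6.3, 6.4, 6.8.1 and the existing research-office sentence. Add one sentence to 6.8.1 stating that the DSMB review after 10 and 20 patients uses AEs from this same window.

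The cost is two sentences of amendment and slightly more form completion. Patients are already observed for this time, so no procedure is added. Recorded AE rates may rise slightly because events now at risk of omission would be counted.

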#### Definity Clinical Safety

Definity is well tolerated and has been used extensively in echocardiography applications [Goldberg et al 2001]. In pre-market clinical trials, Definity was administered to 1716 patients. In these patients 269 (8.4%) reported at least one adverse event. Of these events, 26 were classified as serious including 19 (1.1%) patients experiencing serious cardiopulmonary symptoms including eight deaths. The deaths occurred several days after activated Definity administration and appear to be related to the course of underlying disease. Of the 11 other serious adverse events, which appeared within days of the drug administration (2-15 days), all appeared to be a progression of underlying cardiac and non-cardiac disease. However, a role for Definity in the initiation or course of these adverse events can not be ruled out.

Of the reported adverse reactions following the use of Definity the most frequently reported were headache (2.3%), back and renal pain (2.1%), flushing (1.1%), and nausea (1.0%). Additional risks associated with the contrast material are described in the attached Definity Product insert (Appendix B). All of the non-serious reported side affects have been transient, usually lasting only a few minutes.

Table 1.

Selected Adverse Events Reported in  $\geq 0.5\%$  of the Subjects who Received Definity in Controlled Clinical Studies

No. of Patients Exposed to Definity	1716
No. of Patients Reporting an Adverse Event	269 (8.8%)
Central and peripheral nervous system	54 (3.2%)
Headache	40 (2.3%)
Dizziness	11 (0.6%)
Body as a Whole	41 (2.4%)
Back/Renal Pain	20 (1.2%)
Chest Pain	13 (0.8%)
Digestive System	31 (1.8%)
Nausea	17 (1.0%)
Vascular (extracardiac) disorders	19 (1.1%)
Flushing	19 (1.1%)
Application Site Disorders	11 (0.6%)
Injection Site Reactions	11 (0.6%)

Additional information concerning pre-clinical and clinical experience with Definity, including the dosing levels and reported subject complaints, can be found in the Definity Package Insert that is included as Appendix B.

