### 3.1 Trial Duration

Individual participation in this trial will be limited to US imaging studies (baseline and contrast-enhanced) and a breast biopsy performed up to 30 days after the US study procedures. Baseline and contrast-enhanced images will be acquired on the same day. The entire imaging protocol will require approximately two hours. Subject recruitment is expected to last 3 years (June 2011-2014).

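### The adverse event fields listed in Section 6.8.2 do not show whether an event began before or after the SHI injection, or what SHI volume was given

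*Combined protocol and SAP*

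**What the plan says.** Section 6.8.2 lists the AE form fields. Those on timing and exposure read "date of Definity administration; signs/symptoms and severity; date of onset; date of resolution or death; relationship to the study drug". The list contains no clock time, injection number or Definity volume. The same section adds: "The investigator will evaluate and note the duration, intensity, and relationship to (association with) the Definity administration". Relationship is thus rated against Definity as a whole, not per injection.

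The dosing sequence is in Section 6.3. First, "Following baseline imaging, patients will receive a bolus, IV injection of 0.25 ml of Definity", for pulse inversion HI. Then, "After a 30 minutes waiting period patients will receive a second bolus, IV injection", of up to 20 µl/kg, for SHI. Section 3.1 places this in one visit: "Baseline and contrast-enhanced images will be acquired on the same day", and "The entire imaging protocol will require approximately two hours".

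The Definity Clinical Safety text in the Background says of side effects: "All of the non-serious reported side affects have been transient, usually lasting only a few minutes".

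Section 6.8.1 sets an early DSMB look whose stated purpose is to ensure that the 20 µl/kg "dose used for SHI is not altering the risk benefit ratio, data from the first ten (10) patients and then the next ten patients" being examined as each group finishes. The action rule compares AEs with what the Definity label would lead one to expect.

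**The concern.** The DSMB look is directed at one of the two injections, but the listed fields describe the day. For a short-lived event, the administration, onset and resolution dates will normally all be the same, so they say nothing about order. An event that began and ended in the half hour before the SHI injection would be recorded in these fields just like one that began after it. The SHI volume is written as an upper limit, and Section 6.8.1 allows dosing to be lowered during the trial. The form asks for the dose of concomitant medication but lists none for Definity.

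At stake is a small-sample safety judgement. Events that cannot be due to the SHI dose, because they preceded it, cannot be set aside from these fields, and events cannot be related to the volume each woman received. The same limit would carry into the final safety report. For events that last minutes, times not written down on the day may not be recoverable later.

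**Working it through.** The plan states no figure that bears directly on this point, so the main check sets the sections side by side. The arithmetic only gives scale.

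**1. Can the listed fields order an event against the two injections?**
- Interval between injections: 30 minutes (Section 6.3).
- Whole session: about two hours, on one day (Section 3.1).
- Resolution of the listed timing fields: one day (Section 6.8.2).
- Usual length of non-serious effects: a few minutes (Definity Clinical Safety).

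The recording unit is longer than the whole session, so the dates cannot order events within it. The duration that the investigator notes gives an event's length, not its start relative to either injection. Section 6.8.2 also makes a probable relationship depend on a reasonable temporal association, which these date fields cannot document within one day. No section requires injection or onset times.

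**2. Can the SHI volume be inferred?**
Section 5.1 sets a maximum total of 1.5 ml. If that covers both injections (assumption), 1.5 − 0.25 = 1.25 ml is left for SHI. This equals 20 µl/kg at 1.25 / 0.020 = 62.5 kg, so the volume per kg would be lower in heavier women. The volume given cannot be taken as known unless it is recorded.

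**3. How many events are in play?**
The Background prints 269 of 1716 patients with an AE, as 8.4% in the text and 8.8% in Table 1. The division gives 269 / 1716 = 15.7%. The documents do not settle which figure is wrong, so all three are carried.

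| Rate | Expected in 20 women | Expected in 450 women | Chance of 3 or more in 20 (binomial) |
|---|---|---|---|
| 8.4% | 1.7 | 37.8 | 0.23 |
| 8.8% | 1.8 | 39.6 | 0.26 |
| 15.7% | 3.1 | 70.5 | 0.63 |

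With two or three affected women expected, placing one or two events with the wrong injection could change how the SHI dose is read.

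**4. How far could the SHI rate be overstated if every event were counted against it?**
Inflation = all events / events arising from the SHI injection.
- Risk proportional to volume, at the 1.5 ml maximum (assumption): 1.5 / 1.25 = 1.2-fold.
- Equal risk per injection (assumption): 2 / 1 = 2-fold.

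**5. Would events after the SHI injection be fully recorded?**
Section 6.8.2 records AEs from the start of dosing to the end of administration. Sections 6.4 and 6.8.1 monitor for 30 minutes after contrast. Read literally, an event that began in those 30 minutes after the second injection would be watched for but fall outside the recording window. The passages must be reconciled, or the post-SHI group will be incomplete whatever timing fields are added.

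**The case against.** A reader might infer that the DSMB cannot judge the SHI dose at all. The documents do not support that, for four reasons.

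- **The field list is not exclusive.** It says what the form will include. The DSMB is promised data, not AE forms alone. Data forms, source documents, a drug log and recordings of the examination also exist, and some may carry times.
- **The action rule needs no attribution.** It compares AEs overall with the label. Subjects who complete the trial have had both injections, so the regimen can be judged as given. Counting events from the first injection can only raise the total, which errs towards caution. No section says that they will be charged to SHI.
- **Some events are separable already.** A woman stopped after the first injection is a discontinued subject under Section 6.9.1, with date and reason on the CRF.
- **Clock times are a partial remedy.** An event after the second injection follows both doses, and a split of two or three events has little power.

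All four stand, and they limit the point. They do not remove it. Other records might hold times, but nothing requires them to, and Section 6.8.1 does not say what the DSMB receives. The rule is about overall AEs, but the stated purpose of the look is the SHI dose. Times cannot prove that a later event came from SHI, but they do show which events began before it and so cannot be due to it.

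**Conclusion.** The point holds for the listed fields. As written, they do not show whether an AE began before or after the SHI injection, or what SHI volume was given. The early look can assess the two-injection regimen against the label. From these fields it cannot separate out events that began before the dose it is meant to check.

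The scale is about 1.7 to 3.1 affected women in 20, or 38 to 71 in 450, over the three rates that the Background prints or implies, if those rates apply to this population. If all events were counted against SHI, its apparent rate would be inflated between 1.2-fold and 2-fold. The lower end assumes risk proportional to volume and the upper end equal risk per injection; the documents support neither assumption. A reader might infer a plain doubling, but that is only the upper end, and it assumes equal risk from unequal volumes.

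This is a gap in data capture that is worth closing because the remedy is cheap. It is not evidence that the safety review will fail.

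**What to change.** - **Section 6.8.2, form fields:** record the date and clock time of each injection and of AE onset and resolution, with the injection number and the volume actually given at each injection (ml and µl/kg).
- **Section 6.8.1, DSMB data:** state what the DSMB receives. Split its 10- and 20-patient tables into AEs that began after the first injection and before the second, and AEs that began after the second. Note on the table that the second group follows both doses. Use the same split in the final report.
- **Sections 6.4, 6.8.1 and 6.8.2:** reconcile the AE recording window with the 30-minute monitoring period, so that the second group is complete.
- **Background, Definity Clinical Safety:** reconcile 8.4% and 8.8% with 269 of 1716, since this is the AE background rate quoted in the protocol text.

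The cost is a few CRF fields, one table split and some wording. No procedure, patient or dosing change is involved.
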